**Data Analysis:**

The analyses will be conducted separately in Belgium, Italy and China. Conducting a summarised analysis combining the results of the countries may be considered.

For descriptive statistics, continuous data will be summarised using descriptive statistics (number of non-missing values, mean, median, interquartile range, standard deviation, minimum, and maximum). Categorical data will be summarised using frequency tables

(frequencies and percentages). Time-to-event data will be summarised using the Kaplan-Meier estimate.

From the overall study population, patients will be assigned to the exposure groups (OM-85 or SOC/non-user group) according to whether they received treatment at CED or during the 30-day initiation grace period. Thereafter, PS will be applied to match the OM-85 initiators to comparable SOC/non-user patients, to account for measurable baseline confounding factors between the compared groups. PS of being included in the exposure group initiating OM-85 as opposed to being included in the SOC/non-user group will be estimated for each patient using logistic regression model.

The number and percentage of patients selected into the overall study population, by meeting all the inclusion criteria (no exclusion criteria applied), will be presented for each data source (country) and separated by exposure group. This will be done before and after applying the PS matching (using 1:1 greedy nearest-neighbour method).

The rate of RTI episodes will be estimated by calculating the total number of RTI episodes observed, divided by the total number of person-time (e.g., person-years) during a period of interest. Rates of RTI episodes will be estimated separately in patients initiating preventive treatment with OM-85 and in the SOC/non-user group. Furthermore, rates of RTI episodes during the baseline period will serve as reference in each treatment group to evaluate the effects of therapy during follow-up.

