**Table 4 Inclusion Criteria**

	Inclusion Criteria	Operational Definition
1	Patient aged $\geq 1$ year of age at CED	Aged $\geq 1$ year at CED
2	Patient has $\geq 1$ RTI episodes during the 12-month baseline period prior to CED	$\geq 1$ RTI episodes within a 12-month period during the inclusion period. The CED is the date of the 2 nd , 3 rd , ... or n th RTI episode (i.e., date of fulfilling the inclusion criteria). If one patient has multiple CED during the inclusion period, the CED will be selected randomly. The definition of an RTI episode provided in Section 3.3.2.1
3	Patient has $\geq 12$ months of continuous enrolment in the database prior to CED	$\geq 12$ months of continuous enrolment in the database prior to the CED. Operationally, patients were required to have entered the database at least 12 months before the CED to be included in the study. In THIN (Belgium and Italy), this can be defined by a district variable for entry to the database: first contact date. In Inspur (China), patients are required to have records in the database at least 12 months before the CED (during the 12-month baseline period) to be eligible for inclusion
4	No record of a prescription of any bacterial lysates in the 12-month baseline period prior to CED	No record of the country-specific drug codes ( Appendix 4 ) during the 12-month baseline period

Note: CED: cohort entry date; RTI: respiratory tract infection; THIN: The Health Improvement Network.

Inclusion criterion 2 on the requirement of having  $\geq 1$  prior RTI episodes is important to apply because OM-85 is indicated for prevention of recurrent RTIs (24). However, patients in the SOC/non-user comparator group may still have fewer prior recurrent RTIs than the OM-85 group receiving preventive therapy. Therefore, prior recurrent RTIs will also be used in the PS matching of the compared exposure groups. The impact (preventive effect) of OM-85 on the recurrence of RTIs is anticipated to be higher in patients with an increased recurrence risk (35). Hence, the analyses will also be stratified by the number of RTI episodes prior to CED (see [Table 5](#)).

The inclusion of patients is not defined by sex. Sex is instead defined at CED and considered in the PS.

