#### 3.7.1 General Considerations

For descriptive statistics, continuous data will be summarised using descriptive statistics (number of non-missing values, mean, median, the first quartile, the third quartile, standard deviation [SD], minimum, and maximum). Categorical data will be summarised using frequency tables (frequencies and percentages) among patients with non-missing values.

The number and percentage of missing data will be presented as a separate category for all variables in the descriptive statistics. For the comparative analysis, only observations with complete data will be used. Multiple imputation might be considered for selected variables after the evaluation of missingness. The handling of missing data will be described in more detail in the SAP.

From the overall study population, patients will be assigned to the exposure groups (OM-85 or SOC/non-user group) as detailed in [Section 3.3.1](#). Thereafter, PS will be applied to match the OM-85 initiators to comparable SOC/non-user patients, to account for measurable baseline confounding factors between the compared groups. PS of being included in the exposure group initiating OM-85 as opposed to being included in the SOC/non-user group will be estimated for each patient using logistic regression model. Confounding factors available in the databases will be evaluated for inclusion as covariates in the logistic model, including but not limited to patient demographics, BMI, history of RTI (including upper vs lower), comedications, comorbidities, clinical characteristics, duration of RTI-related hospitalisation(s), and calendar year of CED (see [Section 3.3.3](#); to be detailed in the SAP). Histogram of the PS for both exposure groups will be generated to visually evaluate if there is substantial overlap. Nearest-neighbour matching based on the PS will be used to form pairs of patients from each exposure group that are comparable in baseline confounding factors. The applied matching ratio will be defined in the SAP.

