### 3.7.7 Sensitivity Analyses

The sensitivity analyses will be applied to primary objectives and will be detailed in the SAP. At minimum, the following will be considered:

[figure not shown]
- **Varying maximum length of an RTI episode, for primary outcome definition:** The length of an RTI episode (14 days) will be altered in sensitivity analysis using 7 days and 21 days. The results will inform the robustness for the definition in the main analysis.
- **Censoring at initiation of other bacterial lysates than OM-85:** In both exposure groups, patients are censored at date of the first prescription of another bacterial lysate.

In addition, for primary objective 2, sensitivity analysis will be conducted **implementing clone censor weighting methods on the total population to account for potential immortal time bias and selection bias.** In place of PS matching to set up the study cohort, per protocol analysis implementing methods of clone censor weighting will be implemented. In this method, all patients will be included, not only those that are matched in PS matching, and follow-up will begin at CED. To explain further, at CED, each patient will be cloned and assigned to both an exposed and unexposed (one for each clone) and therefore each patient will have been assigned all treatment strategies at CED or time zero of follow-up. Each clone is then followed during the

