30-day initiation grace period. Patients will be censored from the cloned OM-85 exposed group at the end of the 30-day initiation grace period, if no prescription of OM-85 is observed by then. Patients will be censored from the cloned SOC/non-user group, if a prescription of OM85 is observed during the 30-day initiation grace period (censoring at the date of the prescription). Artificial censoring of the clones when they deviate from their treatment assignment could create potential selection bias due to informative censoring, and thereby inverse probability weighting will be applied to adjust for potential risk of informative censoring, after the CED. The weights are implemented, because not receiving an OM-85 prescription during the 30-day initiation grace period (and thus being censored) is likely not at random, but influenced by variables that could also impact the outcome (confounders) (37). The censoring weighs up the influence of the patients who remain uncensored to account for similar patients who were censored, breaking the association between censoring and variables that may cause the outcome. The variables included in the weighting can include baseline variables and time-varying confounding variables that could change during the 30-day initiation grace period, such as healthcare resource utilisation (e.g. hospitalisation) or receiving a diagnosis of a respiratory condition. Description of baseline as well time-varying variable that change during the initiation grace period will be described and compared in user and non-user groups. The time-varying variables will be selected from the list of baseline factors (as listed above for PS), but they are measured also after CED. These variables will be further defined in the SAP. The cloning and censoring are illustrated in [Figure 3](#).

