#### 3.9.1.2 Objectives Assessed in Both Exposure Groups (Remaining Objectives)

The risk of confounding shall be considered for the objectives that are assessed in both exposure groups:

- Comparative effectiveness design: primary objective 2, secondary objective 4, exploratory objectives CCI
- Descriptive patterns during follow-up in both exposure groups: secondary objectives 5 through 7

In the presence of confounding, the observed results on the outcomes in the compared exposure groups may be due to confounding factors, rather than due to the differing exposure status. Confounding may be a particular challenge in this study, because no active comparator could be identified, as discussed in [Section 3.3.1.1](#).

This risk of confounding will be addressed by matching the compared groups on PS, to emulate randomisation and to enhance the comparability of the exposure groups with regards to their characteristics at CED. Hence, the SOC/non-user group will be restricted to patients with similar prognostic factors and probability of receiving OM-85 during the initiation grace period.

The success of the PS matching (including only measured confounders) will be presented in the descriptive results on baseline characteristics. Similarity of the two exposure groups, i.e., equal distribution of patient characteristics influencing the occurrence of RTI episodes, will relieve uncertainty about the interpretation of the findings. Dissimilarity would warrant cautious interpretations.

As in all non-interventional studies, residual confounding may persist, especially concerning unmeasured confounders (such as lifestyle and health-seeking behaviours), or unknown confounders. Analyses for further addressing confounding analytically and/or investigating the presence of possible confounding (direction and magnitude of anticipated biases) will be considered in the SAP.

It should be noted that for secondary objectives 5-7, on pattern of prescribing antibiotics, concomitant medications of interest, and healthcare resource utilisation, no comparative analyses between the exposure groups will be performed (but may be performed as part of exploratory objectives **CCI**). The descriptive results in both exposure groups separately shall be interested considering possible differences in their baseline characteristics.

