By starting follow-up time at the end of the initiation grace period leads to left truncation, however since mortality due to RTI is low, potential for selection bias due to death in the initiation grace period would be low. Furthermore, it is possible that some patients may not match in PS matching; however, given known indications and contra-indications of OM-85, there should be similar patient characteristics in users and non-users and good overlap of PS to create a match. Sensitivity analysis using CCW methods, however, are planned and will use the entire cohort without exclusion and will have follow-up from CED, which will eliminate left truncation.

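### The matched analysis of primary objective 2 and its clone-censor-weight check target different populations from different time zeros, and the protocol does not say so, so a gap between their overall IRRs cannot be attributed to bias

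*Protocol*

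**What the plan says.** **Main analysis of primary objective 2.** Section 3.7.1 states that "PS will be applied to match the OM-85 initiators to comparable SOC/non-user patients", and runs the comparison in the matched samples only. The synopsis gives the method as "using 1:1 greedy nearest-neighbour method". Section 3.9.1.2 adds that "the SOC/non-user group will be restricted to patients with similar prognostic factors and probability of receiving OM-85 during the initiation grace period". Under Section 3.2.1, follow-up starts at the end of the 30-day initiation grace period.

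**Clone-censor-weight (CCW) sensitivity analysis.** Section 3.7.7 describes it as "implementing clone censor weighting methods on the total population to account for potential immortal time bias and selection bias". It replaces matching, and "all patients will be included, not only those that are matched in PS matching, and follow-up will begin at CED". On the weights it says: "The censoring weighs up the influence of the patients who remain uncensored to account for similar patients who were censored". Section 3.9.3 repeats that the CCW methods "will use the entire cohort without exclusion and will have follow-up from CED", and gives removal of left truncation as a reason.

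**Expected effect and case mix.** The text under Table 4 in Section 3.2.2.1 says: "The impact (preventive effect) of OM-85 on the recurrence of RTIs is anticipated to be higher in patients with an increased recurrence risk". The same paragraph warns that non-users may have fewer prior RTIs than the OM-85 group. Section 3.9.3, in contrast, expects users and non-users to have similar characteristics.

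Table 13 labels the main analysis as modified intention-to-treat and the CCW analysis as per-protocol. It names no target population for either.

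**The concern.** Matching non-users to initiators gives the average effect in the initiators who find a match. Cloning every eligible patient, and weighting uncensored clones up to stand for censored ones, gives the average effect in the whole eligible cohort. Time zero moves by 30 days as well.

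The check exists to show whether the matched result suffers from immortal time or selection bias. When population and time zero change together, a gap between the two IRRs has at least two explanations that involve no bias. With a protective effect that is stronger in high-risk patients, and with more such patients among initiators, both explanations move the CCW result towards 1. A sound matched estimate could then look biased. Offsetting differences could also produce agreement that is taken as reassurance.

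**Working it through.** **1. The plan's own figure.** The protocol gives no size or precision figure for primary objective 2. The only one, Table 9, concerns primary objective 1. With its F-quantile interval, 2 episodes per person-year and 350 person-years per group, b = 700 and a = 0.9 × 700 = 630. The 95% CI width is 0.197, as printed, and all 32 cells of Table 9 reproduce to three decimals. It serves below only as a yardstick.

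**2. Inputs for the two targets.** The documents give the direction of the gradient and the possible direction of the case-mix difference, but no sizes. The split at more than 3 prior RTI episodes is that of Table 5. All of the following are assumptions:
- share with more than 3 prior RTIs: 30–50% of initiators, 10–15% of the cohort;
- IRR 0.70–0.80 in that stratum and 0.95–1.00 in the rest;
- untreated follow-up rates of 3.0 and 1.2 episodes per year.

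**3. Formula.** With p the share in the high stratum (subscript 1) and r the untreated rates,

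overall IRR = [p·r1·IRR1 + (1−p)·r0·IRR0] / [p·r1 + (1−p)·r0].

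The matched target uses the initiators' p and the CCW target uses the cohort's p. Neither calculation contains any bias.

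**4. Results over all corners of the ranges.**

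| Case | Matched target | CCW target | Gap |
|---|---|---|---|
| Smallest gap: p 0.30 vs 0.15, IRRs 0.80/0.95 | (0.720 + 0.798)/1.74 = 0.872 | (0.360 + 0.969)/1.47 = 0.904 | 0.03 |
| Largest gap: p 0.50 vs 0.10, IRRs 0.70/1.00 | (1.05 + 0.60)/2.10 = 0.786 | (0.21 + 1.08)/1.38 = 0.935 | 0.15 |
| Constant IRR 0.80, any p | 0.80 | 0.80 | 0 |
| Same p in both, any IRRs | equal | equal | 0 |

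Across all corners the matched target runs from 0.77 to 0.90 and the CCW target from 0.87 to 0.96.

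**5. Simulation check.** This used 400,000 patients, about 12,000 of them initiators, with 10% of the cohort and 40% of initiators in the high stratum. Untreated rates were 4 and 1.5 per year. There was no unmeasured confounding and no immortal time. 1:1 matching was compared with inverse-probability weighting as a simple stand-in for CCW, over 30 runs. Means were:
- stratum IRRs 0.7 (high) and 0.9: matched 0.772, whole cohort 0.852;
- stratum IRRs 0.7 and 1.0: 0.808 and 0.931;
- constant IRR 0.8: 0.803 and 0.804.

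The run-to-run SD was about 0.01 for each estimate, so gaps of this kind can exceed sampling error in a cohort of that assumed size.

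**6. Time zero.** Assume an even event rate and no effect in the first 30 days, which both clones of a patient largely share. An IRR of 0.70 after the grace period then becomes (30 + 335 × 0.70)/365 = 0.725 over 12 months from cohort entry, and (30 + 700 × 0.70)/730 = 0.712 over 24 months.

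**7. Can the two be aligned?** Let e be the baseline propensity score. Leaving time-varying covariates aside, the censoring weight by the end of the grace period is 1/e for an OM-85 clone and 1/(1−e) for an SOC clone. Multiplying by e gives 1 and e/(1−e), which is the initiators' covariate mix in both arms. The score is already estimated for the matching.

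**The case against.** **The features at issue are deliberate.** Section 3.9.3 names left truncation and unmatched patients as weaknesses of the main design, and uses the whole cohort and the start at cohort entry to address them. This stands. Both features should stay, and the CCW analysis should not be moved to the end of the grace period. That would restore the truncation and come close to a propensity-weighted copy of the main analysis.

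**The gap is conditional.** A reader might infer that the protocol's own expectation forces the two IRRs apart. It does not. Section 3.2.2.1 gives no scale, and a constant IRR already prevents more episodes in patients with higher rates. On case mix it says only that non-users may have fewer prior RTIs, and Section 3.9.3 expects similarity. On the other side, the planned measure is a rate ratio, and Section 3.3.1.1 calls the non-user group heterogeneous in RTI frequency and severity. A check should not need effect homogeneity to be interpretable.

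**The check is not unreadable, nor the only one.** Strata of 1–3 and more than 3 prior episodes are foreseen for all objectives, and comparison within them removes much of the case-mix problem. That help is partial: Section 3.2.2.3 makes subgroup work conditional, no stratified CCW analysis is stated, and one two-level factor does not align the other covariates. Section 3.7.7 also varies episode length and censors at other lysates, but neither of those addresses immortal time or selection.

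**Large weights.** A reader might infer that weighting initiators up to the cohort must be unstable. The documents give neither the initiation share nor the spread of the score. If 2–4% initiate, the mean weight is 1/0.04 to 1/0.02, that is 25 to 50, but this is only scale and cancels in the IRR. The effective sample depends on the assumed spread: about 38–40% of initiators at a logit SD of 1, about 79% at 0.5.

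**Detail for the SAP.** Weighting variables are rightly left there. The population and time zero are fixed in the protocol.

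**Conclusion.** The point holds in a limited form. The protocol fixes the matched analysis on OM-85 initiators and the CCW analysis on all eligible patients from cohort entry, and does not tell the reader that these are different targets. As written, a difference between the overall IRRs cannot be attributed to immortal time or selection bias.

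The possible gap without bias is about 0.03 to 0.15 on the IRR. It rests on assumed stratum shares, IRRs and rates, and needs both a ratio-scale gradient and more prior RTIs among initiators than in the cohort. Without either condition it is nil. For scale, the protocol's own small effect is an IRR of 0.9, which is 0.10 from no effect. The dilution from the earlier start is small, about 0.025 at 12 months for an IRR of 0.70, and assumes no effect in the first 30 days. The documents do not support the stronger conclusions that the check is worthless or that the two results must differ.

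**What to change.** In Section 3.7.7 and Table 13:

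1. State the target population and time zero of each analysis: matched OM-85 initiators from the end of the grace period for the main analysis, all eligible patients from cohort entry for the planned CCW analysis.
2. Add a CCW analysis standardised to OM-85 initiators, with every clone's censoring weight multiplied by the baseline propensity score and follow-up still from cohort entry. Name it as the like-for-like comparison with the matched result. If matching drops initiators, report how many, since this version represents all of them.
3. Keep the total-population CCW analysis and label it as a different target population, so that its difference from the matched IRR is not read as a measure of bias.
4. Optionally, show the standardised version counted from the end of the grace period as an extra step that isolates the time-zero effect. It should not replace the version from cohort entry.

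This needs a few sentences, a few lines of code and no new data. The downside is one or two more columns in the sensitivity table.

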**Figure 3 Illustration of Cloning and Censoring the Treatment Strategies**

Note: CED: cohort entry date; SOC: standard of care

### 3.7.8 [Redacted]

[Redacted]

[Redacted]

[Redacted]

[Redacted]

[Redacted]

[Redacted]

[Redacted]

[Redacted]

[Redacted]

[Redacted]

[Redacted]

[Redacted]

[Redacted]

[Redacted]

[Redacted]

[Redacted]

[Redacted]

[Redacted]

[Redacted]

[Redacted]

[Redacted]

[Redacted]

CCI [Redacted]

CCI [Redacted]

CCI [Redacted]

CCI [Redacted]

CCI [Redacted]

CCI [Redacted]

CCI [Redacted]

CCI [Redacted]

CCI [Redacted]

CCI [Redacted]

CCI [Redacted]

CCI [Redacted]

CCI [Redacted]

CCI [Redacted]

CCI [Redacted]

CCI [Redacted]

CCI [Redacted]

CCI [Redacted]

CCI [Redacted]

CCI [Redacted]

CCI [Redacted]

CCI [Redacted]

CCI [Redacted]

CCI [Redacted]

CCI [Redacted]

CCI [Redacted]

CCI [Redacted]

CCI [Redacted]

CCI [Redacted]

CCI [Redacted]

CCI [Redacted]

CCI [Redacted]

CCI [Redacted]

CCI [Redacted]

general knowledge of OM-85 use and effectiveness among paediatric and adult populations in two geographical areas: Europe and China.

### 3.9.1 Confounding

As in any non-interventional study without randomisation, the risk of confounding must be considered in the study.

#### 3.9.1.1 Before-After Design Among OM-85 Initiators (Primary Objective 1, Secondary Objective 3, Exploratory Objectives CCI)

In the before-after design, differences in the rates of RTI episodes before and after initiation of OM-85 may be caused by factors other than the OM-85 initiation, factors that differ over the compared time periods. Such factors include progression of the patient's health condition (e.g., COPD), changes in the healthcare system or in access to care (opportunities to detect and record outcomes decrease if access to care decreases), and changes in infection rates in the studied population. Therefore, the results must be interpreted with caution.

